6.4.6 Interim Analyses

Safety Reviews: The PSRT will review safety data routinely throughout the study. The study will utilize both electronic database features and reviews by designated safety review personnel to identify in a timely manner if any of the safety pause rules of the study are met.

Immunogenicity Review: Analyses of immunogenicity may be performed when pseudo-neutralization assay of samples collected 2 weeks after each vaccination are conducted. This may occur prior to completion of safety follow-up visits or collection of data for secondary and exploratory immunogenicity endpoints. Such an analysis would constitute the final analysis for the primary immunogenicity endpoint, so sample size adjustments are not required. Reports providing results by study group may be provided to VRC solely for the purpose of informing decisions related to future trials in a timely manner. The results should in no way influence the conduct of the VRC 321 trial in terms of early termination or later safety or immunogenicity endpoint assessments. Analyses of secondary and exploratory immunogenicity assays may also be performed as data become available.

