1.6 ASSESSMENT OF VACCINE IMMUNOGENICITY

In this study, specimens to evaluate immunogenicity will be collected at baseline and at specified time points. The primary immunogenicity time point is two weeks after the first vaccination and assessed by measuring HA stem-specific antibody by pseudo-neutralization assay. Additional assessment of HA stem-specific antibody measured by pseudo-neutralization assay will be conducted on stored samples obtained throughout the study.

Exploratory evaluations will include measurements of human ferritin antibody and *H. pylori* ferritin antibody. Additional exploratory evaluations may include the detection of antibody by MSD (Meso Scale Delivery) or neutralization assay, and exploratory B and T cell assays.

Research samples for immunogenicity assays will be processed by the Vaccine Immunology Program (VIP) in Gaithersburg, MD, where many of the immunogenicity assays will also be performed. Some immunogenicity assays may be performed by VRC laboratories in Bethesda, MD, or by approved contract laboratories or research collaborators.

Results from this study are expected to provide a foundation for development of a universal influenza vaccine candidate as well as show proof-of-concept for elicitation of antibody responses by influenza HA stem vaccination.

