3.2 SECONDARY OBJECTIVES

- To evaluate the antibody response to the VRC-FLUNPF099-00-VP vaccine administered as a single dose at 20 mcg IM via needle and syringe at two weeks after injection.
- To evaluate the antibody response to the VRC-FLUNPF099-00-VP vaccine administered as repeat dosing at 60 mcg IM via needle and syringe at two weeks after each injection.

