6.2.2 Secondary Endpoints: Immunogenicity

The principal immunogenicity endpoints will be assessed by measuring HA-stem specific antibody by pseudo-neutralization assay at:

- Group 1: Baseline (Week 0/Visit 02) and Week 2 (Visit 04) after vaccination, and
- Groups 2A-2D: Baseline (Week 0/Visit 02) and Week 2 (Visit 04) after the first vaccination, and at Week 16 (Visit 07) and Week 18 (Visit 09) after the second vaccination

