6.3.2 Power Calculations for Immunogenicity

Table 6-1 gives the probabilities of observing 0 or more than 1 response over a range of underlying response rates and different sample sizes.

Table 6-2 is applicable to the immunogenic response rates and gives the exact 95% confidence interval of the true response rate over possible number of responses out of the 5 and 12 subjects.

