6.4 STATISTICAL ANALYSIS

All statistical analyses will be performed using Statistical Analysis System (SAS), R, or S-Plus statistical software. No formal multiple comparison adjustments will be employed for safety endpoints or secondary endpoints.

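### The plan leaves unclear which immunogenicity analysis is the final primary one, and it specifies no pooled response rate or interval for the 60 mcg regimen

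*Combined protocol and SAP*

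**What the plan says.** **Time point.** Section 1.6: "The primary immunogenicity time point is two weeks after the first vaccination". It treats other pseudo-neutralization time points as additional assessment. Section 6.4.6: "Analyses of immunogenicity may be performed when pseudo-neutralization assay of samples collected 2 weeks after each vaccination are conducted", and then "Such an analysis would constitute the final analysis for the primary immunogenicity endpoint, so sample size adjustments are not required". The same paragraph separates that endpoint from the secondary and exploratory immunogenicity endpoints. Section 6.2.2 is headed as secondary endpoints and opens "The principal immunogenicity endpoints will be assessed by measuring HA-stem specific antibody by pseudo-neutralization assay at". For Groups 2A-2D it lists visits around both doses (post-dose Visits 04 and 09) and does not rank them.

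**Unit of estimation.** The second objective in Section 3.2 concerns the antibody response to the vaccine "administered as repeat dosing at 60 mcg IM via needle and syringe at two weeks after each injection". It is written for the regimen, not for an age group. Section 6.3.2 says that Table 6-2 "gives the exact 95% confidence interval of the true response rate over possible number of responses out of the 5 and 12 subjects". Section 6.4.4 analyses subjects by assigned group and presents response rates with exact 95% intervals. Early reports under 6.4.6 are by study group. Table 6-1 has a column for the four 60 mcg groups combined (N=48), and its title covers immunogenicity as well as safety. That table gives only the chance of seeing no event or more than one.

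**Multiplicity.** Section 6.4: "No formal multiple comparison adjustments will be employed for safety endpoints or secondary endpoints".

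**The concern.** Section 6.4.6 justifies looking at immunogenicity before the study ends on one ground: the look is the final analysis of the primary immunogenicity endpoint. That works only if the endpoint is fixed. Under Section 1.6 a Week 2 analysis completes it. If the endpoint covers samples taken after each vaccination, as 6.4.6 can be read, it is not complete until Week 18. Section 6.2 does not resolve this, because it defines no primary immunogenicity endpoint.

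The second gap is one of estimation. All 48 subjects in Groups 2A-2D are planned to receive the same 60 mcg regimen, and the objective asks how that regimen performs. The intervals set out are for 12 subjects at a time.

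The study is open-label, Section 4 states the hypothesis that the vaccine will induce an antibody response, and by-group results may be released early to inform future trials. It should therefore be plain beforehand which result answers the question.

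**Working it through.** **1. The sections side by side**

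| Section | Status given to the assay | Post-dose time points, 60 mcg |
|---|---|---|
| 1.6 | primary time point | Week 2 |
| 6.2.2 | secondary, called principal | Weeks 2 and 18, unranked |
| 6.4.6 | primary, distinct from secondary | two weeks after each vaccination, i.e. Weeks 2 and 18 |
| 3.2 | secondary objective | two weeks after each injection |

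Week 2 appears in every row, so the versions overlap. They differ on whether Week 18 belongs to the primary endpoint. In Appendix I, Visit 04 is Day 14 and Visit 09 is Day 126. The point at which a subject's data are complete for the final analysis therefore moves by 126 - 14 = 112 days, or 16 weeks.

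**2. Count of 60 mcg results.** Four age groups × two post-dose visits = 8 group-level results. Group 1 adds one at 20 mcg. A pooled analysis would add one 60 mcg result per visit, two in all. None is specified.

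**3. Reproducing Table 6-2.** The exact (Clopper-Pearson) limits for x responders of n are:
- lower = 2.5% quantile of Beta(x, n-x+1), set to 0 if x = 0
- upper = 97.5% quantile of Beta(x+1, n-x), set to 1 if x = n

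All 19 rows reproduce to three decimals, for example 6/12: 0.211-0.789 and 12/12: 0.735-1. The plan's own figures are correct.

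**4. The same formula at n = 48.** The documents give no expected response rate, so a range is shown. Widths come from unrounded limits.

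| Observed rate | n = 12 | Width | n = 48 | Width |
|---|---|---|---|---|
| 25% | 0.055-0.572 | 0.517 | 0.136-0.396 | 0.260 |
| 50% | 0.211-0.789 | 0.578 | 0.352-0.648 | 0.295 |
| 75% | 0.428-0.945 | 0.517 | 0.604-0.864 | 0.260 |
| 92% | 0.615-0.998 | 0.383 | 0.800-0.977 | 0.177 |
| 100% | 0.735-1 | 0.265 | 0.926-1 | 0.074 |

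At 50% the width ratio is 0.295/0.578 = 0.51. At 92% it is 0.177/0.383 = 0.46.

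**5. How much room for selection the time-point ambiguity adds.** Suppose all 60 mcg groups share one true rate at both visits. With F the binomial (n = 12) distribution function, the expected highest of k independent observed rates is (1/12) Σ [1 - F(x)^k], summed over x = 0 to 11.

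| True rate | Highest of 4 (one visit) | Highest of 8 (either visit) | Added |
|---|---|---|---|
| 0.5 | 0.647 | 0.702 | 0.055 |
| 0.7 | 0.831 | 0.876 | 0.045 |
| 0.9 | 0.977 | 0.994 | 0.017 |

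The two visits share subjects, so the added amount is an upper-end figure. Most of the gap between the highest result and the true rate is already present with four age groups at one visit.

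**The case against.** **The sections can be reconciled.** Section 6.4.6 is permissive and speaks of analyses in the plural. It can be read as one analysis after each dose, each final for its own time point. No section names Week 18 in place of Week 2. This stands as a reasonable reading, but the text then speaks of a single primary endpoint and does not say so. The fix makes that reading explicit.

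**Pooling is not excluded.** A reader might infer that the plan allows intervals only by age group. The documents do not support that. In 6.4.4, analysis by assigned group states the intent-to-treat principle and is set against analysis by the vaccination actually received. Table 6-2 is sample-size material, and Table 6-1 already has an N=48 column. What stands is an omission.

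**Age-group results are intended.** Section 1.5 stratifies the higher-dose group in order to see how responses vary with age. Demoting those estimates would cut against the design. This stands in full.

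**There is no error rate to inflate.** A reader might treat nine unadjusted intervals (Group 1 at Week 2, plus eight at 60 mcg) as a multiplicity failure. At a common true rate of 0.5, a 12-subject lower limit exceeds the truth only at 10/12 or more: probability (66 + 12 + 1)/4096 = 0.0193. Group 1 cannot contribute, since its highest lower limit is 0.478. Four groups at Week 2 give 1 - (1 - 0.0193)^4 = 7.5%. All eight 60 mcg results, if independent, give 1 - (1 - 0.0193)^8 = 14.4%. So about half of that figure comes from the intended age strata alone. Above a true rate of 0.735, the highest lower limit in Table 6-2, it is exactly zero. Immunogenicity is a secondary objective with no success threshold, and 6.3.3 labels the between-group comparisons exploratory and unpowered. This objection stands.

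**Conclusion.** The concern holds in two limited parts. First, Sections 1.6, 6.2.2 and 6.4.6 do not agree on what the primary immunogenicity endpoint is, so it is unclear whether the analysis called final is complete at Week 2 or only at Week 18. This rests on the text alone. Second, no pooled 60 mcg response rate or interval is specified, although the objective is written for that regimen. Specifying one would cut the interval width by about half over observed rates of 25% to 92%, and by more at 100%.

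The precision figures assume a binary readout and full groups of 12. Section 6.4.4 removes subjects who are antibody-positive at baseline and the documents give no expected proportion, so the analysed numbers may be smaller at both levels.

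The consequence is selective reading and avoidable imprecision. It does not touch the primary safety objective, and no formal error rate is affected.

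**What to change.** 1. Align 6.2.2 and 6.4.6 with 1.6. Week 2 (Visit 04) is the primary immunogenicity time point, and Week 18 (Visit 09) is the next-ranked secondary one. State in 6.4.6 that each early analysis is final only for its own time point, once all samples for that visit have been assayed.
2. In 6.4.4, add a response rate for Groups 2A-2D combined (N=48, less any excluded baseline-positive subjects) with an exact 95% interval. Give it at both Week 2 and Week 18, because objective 3.2 asks for the response after each injection. Add N=48 to Table 6-2 and refer to it in 6.3.2.
3. Keep the four age-group estimates beside the pooled one, as Section 1.5 requires.

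The cost is wording in four sections and one table column, with no new samples, assays or subjects. The drawback is that the pooled rate averages over age groups that may differ, and weights them by size if exclusions or extra enrolment make them unequal. Showing the age-group results alongside deals with this.

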7. PHARMACY AND ADMINISTRATION PROCEDURES

The study groups and study agent dosing schedule are shown in **Table 1** in **Section 4**. Refer to the IB for further information about the investigational study products.

7.1 STUDY PRODUCT

The study includes one investigational vaccine described as follows:

- VRC-FLUNPF099-00-VP at 180 mcg/mL. Vials contain 0.7 ± 0.1 mL of a clear, colorless, isotonic buffered (pH=7.2) sterile solution. The formulation buffer consists of 20mM Sodium Phosphate, 100mM Sodium Chloride, 5% Sucrose, and 0.01% PF-68. Vials are intended for single use only and do not contain a preservative. Vials must not be refrozen or reused after thawing.
- VRC-PBSPLA043-00-VP (PBS), diluent, is a clear, colorless, sterile solution at pH 7.2, aseptically filled to a volume of 1.2 mL in a 3 mL glass vial. Vials are intended for single use only and do not contain preservative. Vials must not be refrozen or reused after thawing.

7.2 STUDY PRODUCT PRESENTATION AND STORAGE

7.2.1 Study Product Labels

At the time of study product delivery to the pharmacy, labels on study products VRC-FLUNPF099-00-VP and VRC-PBSPLA043-00-VP will have specific product information (e.g., product description, VRC product number, lot number, fill volume, concentration, fill date, storage condition). Labels will contain an Investigational Use Statement (“Limited by Federal Law to Investigational Use”) and manufacturer information.

7.2.2 Study Product Storage

VRC-FLUNPF099-00-VP (H1ssF 3928): Vials will be shipped within the recommended temperature range using appropriate shipping configurations to the study pharmacist or designee. Vials of vaccine are stored until use at -35°C to -15°C in a qualified, continuously monitored, temperature-controlled freezer. As freezer temperatures may fluctuate, a temperature range of -45°C to -10°C is acceptable. Storage below -45°C is not permitted because of the stopper limitation.

VRC-PBSPLA043-00-VP (PBS): Vials are stored until use at the target temperature of -35°C to -15°C in a qualified, continuously monitored, temperature-controlled freezer. As freezer

temperatures may fluctuate, a temperature range of -45°C to -10°C is acceptable based upon historic stability data from studies of similar products.

7.2.3 Temperature excursions

If deviations in storage temperature occur from the normal allowance for the pharmacy freezer, the site pharmacist or designee must report the storage temperature excursion promptly to the PI and IND Sponsor. The excursion must be evaluated and investigated, and action must be taken to restore and maintain the desired temperature limits. Pending the outcome of the investigation, the IND Sponsor will notify the pharmacist if continued clinical use of the product is acceptable.

7.3 PREPARATION OF STUDY PRODUCTS FOR INJECTION

This section describes how the site pharmacist will prepare study injections. Clinician instructions on how to select an arm and administer an injection are in Section 4.2.5. Refer to the group assignment for the study subject to prepare the correct dose.

For all study groups, the prepared syringe must be labeled with the subject identifier and the date and time after which the preparation may not be used. Filled syringes should be kept at room temperature and out of direct sunlight until product administration. All injections must be administered within 4 hours after removing the vaccine vial from the freezer.

7.3.1 Preparation of VRC-FLUNPF099-00-VP for Needle and Syringe Administration

Subjects will receive the vaccine via needle and syringe injection. The following instructions apply for VRC-FLUNPF099-00-VP preparation. More information on vaccine preparation is available in the IB.

Group 1 (20 mcg):

1. Thaw 1 vial of H1ssF_3928 at room temperature (15 to 30° C) until all ice crystals have melted. Swirl gently to mix.
2. Thaw 1 vial of PBS diluent at room temperature (15 to 30° C) until all ice crystals have melted. Swirl gently to mix.
3. Withdraw 0.11 mL of H1ssF_3928 into the syringe.
4. Withdraw 0.2 mL of PBS into the same syringe.
5. Invert syringe 5x to mix.

Group 2A, Group 2B, Group 2C, and Group 2D (60 mcg):

1. Thaw 1 vial of H1ssF_3928 at room temperature (15 to 30° C) until all ice crystals have melted. Swirl gently to mix.
2. Withdraw 0.33 mL of H1ssF_3928 into the syringe.

7.3.2 Administration of Injections

Refer to Section 4.2.5. Product labeling and IM injection procedures will be performed consistent with institutional policies and standard procedures.

7.4 STUDY PRODUCT ACCOUNTABILITY

7.4.1 Documentation

The study pharmacist or designee will be responsible for maintaining an accurate record of the codes, inventory, and an accountability record of the investigational study products supplies for this study. Electronic documentation as well as paper copies will be used.

7.4.2 Disposition

The empty vials, the partially-used vials, and any unused, unopened vial that has been removed from freezer will be discarded on the same day as removal from freezer in a biohazard containment bag and incinerated or autoclaved per facility policy. Any unopened vials that remain at the end of the study will be discarded or returned at the discretion of the VRC in accordance with policies that apply to investigational products. Partially used vials or expired prepared doses cannot be administered to other subjects nor used for *in vitro* experimental studies and will be discarded as indicated above.

8. HUMAN SUBJECT PROTECTIONS AND ETHICAL OBLIGATIONS

This research study will be conducted in compliance with the protocol, International Council for Harmonisation Good Clinical Practices (ICH-GCP) guidance, and all applicable regulatory requirements.

8.1 INSTITUTIONAL REVIEW BOARD

A copy of the protocol, ICF, other written subject-facing information, and any advertising material will be submitted to the NIAID IRB for written approval prior to use.

The PI must submit and, where necessary, obtain approval from the IRB for all subsequent protocol amendments and changes to the ICF. The PI will notify the IRB of events that occur on study as described in Section 5.4.

The investigator will be responsible for obtaining IRB approval of the annual Continuing Review throughout the duration of the study.

8.2 SUBJECT IDENTIFICATION AND ENROLLMENT OF STUDY PARTICIPANTS

Study subjects will be recruited through on-site and off-site advertising done for the screening protocol, VRC 500 (11-I-0164). All study activities will be carried out at the NIH CC. Effort will be made to include women and minorities in proportions similar to that of the community from which they are recruited.

8.2.1 Participation of Children

Children are not eligible to participate in this clinical trial because the investigational vaccine has not been previously evaluated in adults. If the product is assessed as safe and immunogenic, other protocols designed for children may be conducted in the future.

8.2.2 Participation of NIH Employees

NIH employees and members of their immediate families may participate in this protocol. NIH staff may be a vulnerable class of subjects. The VRC will follow the Guidelines for the Inclusion of Employees in NIH Research Studies and will give each employee a copy of the “NIH Information Sheet on Employee Research Participation” and a copy of the “Leave Policy for NIH Employees Participating in NIH Medical Research studies.”

Neither participation nor refusal to participate will have an effect, either beneficial or adverse, on the participant’s employment or work situation. The NIH information sheet regarding NIH employee research participation will be distributed to all potential subjects who are NIH employees. The employee subject’s privacy and confidentiality will be preserved in accordance

with NIH CC and NIAID policies. For NIH employee subjects, consent will be obtained by an individual who is independent of the employee's team. If the individual obtaining consent is a co-worker to the subject, independent monitoring of the consent process will be included through the Bioethics Consultation Service. Protocol study staff will be trained on obtaining potentially sensitive and private information from co-workers or subordinates.

8.3 INFORMED CONSENT

The study ICF describes the investigational product to be used and all aspects involved in protocol participation.

Before a subject's participation in the study, the investigators must obtain written informed consent from the subject, after adequate explanation of the aims, methods, anticipated benefits, and potential hazards of the study and before any protocol-specific procedures or study products are administered.

An IRB-approved AoU, intended to assist in the evaluation of the subject's understanding of this study, is administered as part of the consent process.

The acquisition of informed consent will be documented in the subject's medical records, as required by 21 CFR 312.62, and the ICF will be signed and personally dated by the subject and by the person who conducted the informed consent discussion. The original, signed ICF will be placed in the medical record and a copy of the signed ICF will be provided to the subject.

8.4 SUBJECT CONFIDENTIALITY

The investigator must ensure that the subject's anonymity is maintained and will ensure that no information identifying the subject will be released to any unauthorized party. Subjects will not be identified in any reports on this study. All records will be kept confidential to the extent provided by federal, state and local law. Medical records are made available for review when required by the FDA or other authorized users, such as the vaccine manufacturer, only under the guidelines set by the Federal Privacy Act. Direct access includes examining, analyzing, verifying, and reproducing any records and reports that are important to the evaluation of the study. The investigator is obligated to inform the subjects that the above-named representatives will review their study-related records without violating the confidentiality of the subjects. Stored study research samples are labeled by a code (such as a number) that only the study team can link to the subject. The requirement to maintain subject confidentiality is discussed in the study ICF.

8.5 RISKS AND BENEFITS

8.5.1 Risks of the VRC-FLUNPF099-00-VP vaccine

This is the first study in humans of the investigational vaccine, VRC-FLUNPF099-00-VP. This product is derived from *H. pylori* ferritin and not human ferritin, for this reason it is not expected to interfere with iron storage, transport or iron serum levels [18].

Potential side effects resulting from IM injection include stinging, arm discomfort, redness of the skin or mild bruising at vaccine injection sites.

Subjects may exhibit general signs and symptoms associated with administration of a vaccine, including fever, chills, rash, aches and pains, nausea, headache, dizziness and fatigue. These side effects will be monitored, but are generally short term, mild to moderate severity and

usually do not require treatment.

In another VRC study of a similar ferritin vaccine (VRC 316), only 23.4% of participants were noted to have occasional asymptomatic and self-limited changes in laboratory tests such as mild leukocytosis, mild leukopenia, and mild increase in ALP as of March 24, 2019.

There may be other unknown side effects.

